
Name of the sponsor: I.R.I.S.	Individual Study Table Referring to Part of the Dossier	(For National Authority Use only)
Name of Finished Product: Not applicable	Volume:	
Name of Active Ingredient: S64315 (also named MIK665) Azacitidine	Page:	

Anti-emetic prophylaxis
 
Anti-emetic prophylaxis is strongly recommended prior to S64315 infusion and azacitidine administration to mitigate the risk of gastro-intestinal side effects. For more details, see section 8.2.8.1.
 
Tumour Lysis Syndrome (TLS) prophylaxis
 
TLS prophylaxis is required during each administration of IMPs for patients with active disease, in case of inpatient dose escalation to a new assigned dose and in case of readministration after IMP interruption ≥ 28 days. TLS preventive strategies will start the day before the first S64315 infusion of the LID period. In addition to the recommendations described in the protocol, management of TLS will be based on international guidelines and published criteria (Cairo, 2010). For more details see section 8.2.9.
 
Infusion related reaction (IRR) prophylaxis
 
IRR prophylaxis is proposed prior to S64315 infusions. For more details, see section 8.2.10.
 
IMP administration/readministration criteria
 
Criteria to fulfil before each S64315 administration
 
 - Before each S64315 infusion, all biological parameters should be checked in order to detect any toxicity (see Table (4.1.3.5) 1 and Table (8.12) 1). - Patients with Grade ≥ 2 hypo/hypercalcemia and/or hypo/hypermagnesia and/or hypo/hyperkalaemia despite attempts at medical correction should not be treated with S64315 - Patients with white blood cell (WBC) count ≥ 10 G/L despite attempts at medical correction should not be treated with S64315. Hydroxycarbamide or leukapheresis may be used to reduce the circulating blast count before and throughout the study. WBC count must be checked twice a week during the LID period in order to maintain the WBC < 10 G/L - AST and ALT ≤ 3 x ULN (except for LID1: AST and ALT ≤ 1.5 x ULN) - Total bilirubin level ≤ 1.5 x ULN, except for patients with known Gilbert's syndrome, who are excluded if total bilirubin > 3.0 x ULN or direct bilirubin > 1.5 x ULN - In the case of an S64315 interruption ≥ 28 days, its readministration must be preceded by a lead-in dose period (except for patients in CR/CRi). For more details, see section 6.1.2. 
Criteria to fulfil before each first azacitidine administration (i.e. CXD1)
 
Patients should be monitored for haematological toxicity and renal toxicities. A delay in starting the next cycle or a dose adjustment due to haematological toxicity and/or renal toxicity may be necessary according to azacitidine E.U. SmPC (see Table (8.12) 2). WBC, absolute neutrophil count (ANC), platelets, serum creatinine, blood urea nitrogen (BUN) and serum bicarbonate will be assessed before starting the next treatment cycle.
		

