6.1.2. Administration/re-administration criteria

- Criteria to fulfil before each S64315 infusion
 - Before each S64315 infusion, biological parameters should be checked in order to detect any toxicity (see [Table \(8.12\) 1](#))
 - Patients with Grade ≥ 2 hypo/hypercalcemia and/or hypo/hypermagnesia and/or hypo/hyperkalaemia despite attempts at medical correction should not be treated with S64315
 - Patients with WBC ≥ 10 G/L despite attempts at medical correction should not be treated with S64315. Hydroxycarbamide can be used to reduce the circulating blast count before and throughout the treatment period
 - AST and ALT ≤ 3 x ULN (except for LID1: AST and ALT ≤ 1.5 x ULN)
 - Total bilirubin level ≤ 1.5 x ULN, except for patients with known Gilbert's syndrome, who are excluded if total bilirubin > 3.0 x ULN or direct bilirubin > 1.5 x ULN
 - In the case of an S64315 interruption ≥ 28 days, its readministration must be preceded by a lead-in dose period (except for patients in CR/CRi) which is called additional Lead-In dose period. See [Table \(4.1.2\) 1](#) for more details on safety assessments required.
- Criteria to fulfil before each first azacitidine administration (i.e. CxD1)

Patients should be monitored for haematological toxicity and renal toxicities. A delay in starting the next cycle or a dose adjustment due to haematological toxicity and/or renal toxicity may be necessary according to E.U. SmPC (see [Table \(8.12\) 2](#)). WBC, absolute neutrophil count (ANC), platelets, serum creatinine, BUN and serum bicarbonate will be assessed before starting the next treatment cycle.

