8.12. Management of treatment dose adaptations due to toxicities

For patients who do not tolerate the protocol-specified dosing schedule, dose interruptions and/or reductions are either recommended or mandated in order to allow patients to continue the study treatments.

Dose modifications recommendations for S64315 are summarised in [Table \(8.12\) 1](#).

A patient must discontinue treatment with S64315 if, after treatment is resumed at a lower dose, the toxicity recurs with the same or worse severity, unless in the opinion of the investigator it is in the patient's best interest to continue S64315, and upon documented agreement with the Sponsor.

For each patient, once a dose reduction has occurred, the dose may not be re-escalated during the subsequent cycles unless in the opinion of the investigator it is in the patient's best interest to continue S64315, and upon documented agreement with the Sponsor.

When a patient meets the criteria for S64315 discontinuation described in the table, he/she must discontinue both IMPs.

Dose modifications for azacitidine must be done according to azacitidine E.U. SmPC (see [Table \(8.12\) 2](#)).

These dose changes must be recorded in the eCRF.

Table (8.12) 1 - Criteria for interruption and re-initiation of S64315

Recommended dose modifications for S64315	
Worst toxicity CTCAE Grade^a (unless otherwise specified)	During a cycle of therapy
Investigations (Renal)	
Serum creatinine	
Grade 2 (> 1.5 – 3 x ULN or > 1.5 – 3 x baseline)	Omit dose until resolved to Grade ≤ 1 or baseline, then: - If resolved in ≤ 14 days, then maintain dose level - If resolved in > 14 days, then ↓ 1 dose level
Grade 3 (> 3 – 6 x ULN or > 3 x baseline)	Omit dose until resolved to Grade ≤ 1 or baseline, then ↓ 1 dose level
Grade 4 (> 6 x ULN)	Discontinue patient from test drug treatment
Note: If intercurrent illness, e.g. dehydration due to diarrhoea or febrile infections, leads to prerenal insufficiency, this should not be considered drug related and the criterion for dose modification not fulfilled	
Investigations (Hepatic)	
Isolated Total Bilirubin elevation^b	
Grade 2 (> 1.5 - 3.0 x ULN if baseline was normal, >1.5 - 3.0 x baseline if baseline was abnormal)*	Omit dose until resolved to Grade ≤ 1, then: - If resolved in ≤ 14 days, maintain dose - If resolved in > 14 days, ↓ 1 dose level

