Grade 3 (> 3.0 - 10.0 x ULN)	Omit dose until resolved to Grade ≤ 1, then: - If resolved in ≤ 14 days, ↓ 1 dose level - If resolved in > 14 days, discontinue patient from test drug treatment The patient should be weekly monitored (including Liver Function Tests (LFT) ^f), or more frequently if clinically indicated, until total bilirubin has resolved to baseline or stabilised over 4 weeks
Grade 4 (> 10.0 x ULN)	Discontinue patient from test drug treatment The patient should be weekly monitored (including LFT), or more frequently if clinically indicated, until total bilirubin has resolved to baseline or stabilised over 4 weeks
Isolated AST or ALT elevation	
AST or ALT > 3.0 – 5 x ULN	Omit dose S64315 until resolved to ≤ 3 x ULN, then maintain dose
Grade 3 (> 5.0 - 20.0 x ULN if baseline was normal; >5.0 - 20.0 x baseline if baseline was abnormal)	Omit dose until resolved to ≤ 3 x ULN, then: - If resolved in ≤ 14 days, maintain dose - If resolved in > 14 days, ↓ 1 dose level.
Grade 4 (> 20.0 x ULN if baseline was normal; >20.0 x baseline if baseline was abnormal)	Discontinue patient from test drug treatment

Combined^c elevations of AST or ALT and total bilirubin^e

AST or ALT > 3.0 x ULN combined with total bilirubin > 2.0 x ULN and confirmed Hy's law cases according to FDA guidance

- For patients with normal baseline ALT or AST or total bilirubin value
 - If AST or ALT > 3.0 x ULN combined with total bilirubin > 2.0 x ULN without evidence of cholestasis^d:
 - Permanently discontinue patient from test drug treatment For patients with elevated baseline AST or ALT or total bilirubin value
 - If [AST or ALT > 2.0 x baseline AND > 3.0 x ULN] OR [AST or ALT > 8.0 x ULN], whichever is lower, combined with [total bilirubin > 2.0 x baseline AND > 2.0 x ULN]:
 - Permanently discontinue patient from test drug treatment.
- Repeat LFT^f as soon as possible, perform liver imaging to assess biliary tract or liver disease (if possible), preferably within 48h from awareness of the abnormal results, then with weekly monitoring of LFT^f, or more frequently if clinically indicated, until AST, ALT or bilirubin has resolved to baseline or stabilised over 4 weeks

Investigation (Pancreatic)**Amylase and/or lipase elevation**

Grade 1 (> ULN - 1.5 x ULN)	May maintain dose level
> 1.5 - 2.0 x ULN	May maintain dose level

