Grade 3	Omit dose until resolved to Grade ≤ 1, and increase ophthalmic monitoring frequency to at least once a week, and refer the patient to an ophthalmologist within one week for further evaluation, then: 
 - If resolved in ≤ 14 days, ↓ 1 dose level - If resolved in > 14 days, discontinue patient from test drug treatment
Grade 4	Discontinue test drug treatment and refer the patient to an ophthalmologist for monitoring
Haematological abnormalities (myelosuppression)	
Neutropenia and thrombocytopenia Grade 4	If bone marrow clearance, omit dose and/or interrupt azacitidine until count recovery: 
 - If resolved in < 28 days, then maintain the dose level - If resolved in > 28 days, then consider discontinuing patients from study unless the patient has evidence of clinical benefit and in discussion with the Sponsor a decision is made to continue therapy at a lower dose
Other AEs	
Grade 3	If Grade 3 (except those correctable within 7 days and deemed by the investigator to be not clinically important), hold treatment until resolved to Grade ≤ 1 or baseline, then: 
 - If resolved in ≤ 14 days, ↓ 1 dose level - If resolved in > 14 days, discontinue patient from test drug treatment
Grade 4	Discontinue test drug treatment
NOTE In some particular cases, a patient with a Grade 3 or Grade 4 AE may resume treatment at the lower dose level if in the opinion of the Investigator and after discussion with the Sponsor, the event is not life-threatening, and the patient can be managed and monitored for recurrence of the AE. In case of TLS Grade 3 or 4, the dose adaptation of the study drugs will be discussed between the sponsor and the investigator according to the patient's benefit/risk assessment.	

All dose modifications should be based on the worst preceding toxicity.

Patients may receive supportive care (e.g. packed red blood cells) as per local institutional guidelines.

^a Common Toxicity Criteria for Adverse Events (CTCAE v5.0)

^b If Grade 3 or 4 hyper-bilirubinaemia is due to the indirect (non-conjugated) component only, and haemolysis as the aetiology has been ruled out as per institutional guidelines (e.g. review of peripheral blood smear and haptoglobin determination), then ↓ 1 dose level and continue treatment at the discretion of the investigator

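### Footnote b of Table (8.12) 1 permits S64315 to continue in an indirect-only Grade 3–4 bilirubin rise, while section 6.1.2 bars the infusion if the rise persists at dosing; precedence is not stated

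*Protocol*

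**What the plan says.** Two parts of the protocol govern whether S64315 is given when bilirubin is raised.

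**The pre-infusion criteria.** Section 6.1.2 has a list headed "Criteria to fulfil before each S64315 infusion"; the synopsis repeats it as "Criteria to fulfil before each S64315 administration". Both include "Total bilirubin level ≤ 1.5 x ULN". The one exception is for patients with known Gilbert's syndrome, "who are excluded if total bilirubin > 3.0 x ULN or direct bilirubin > 1.5 x ULN". Neither list mentions a rise confined to the indirect component.

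**The dose-modification table.** Table (8.12) 1 has a block titled "Isolated Total Bilirubin elevation", and footnote b is attached to that title. The block says:
- "Grade 3 (> 3.0 - 10.0 x ULN"): hold S64315 until recovery to Grade 1 or lower. Then go down one level if recovery took 14 days or less, or discontinue if it took longer.
- Grade 4 (above 10.0 x ULN): discontinue.

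Footnote b modifies both rows. If the Grade 3 or 4 rise is indirect only and haemolysis has been excluded, the instruction is one step down in "dose level and continue treatment at the discretion of the investigator". It states no recovery threshold and does not refer to section 6.1.2.

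**The concern.** Footnote b applies only above 3.0 x ULN, and section 6.1.2 stops infusions at or below that level. A site working from the footnote could infuse at the reduced dose while bilirubin is still raised. A site working from the pre-infusion list would withhold the same infusion.

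Hepatic toxicity is one of the identified risks in Table (8) 1, with its own monitoring in section 8.2.6, so inconsistent handling between sites matters. Deviation reporting is affected too. Section 14.2 permits no protocol deviations, and SAP section 4.2.1.2 has categories for incorrect treatment or dose and for safety possibly affected. The same infusion could be compliant under one passage and a deviation under the other.

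**Working it through.** There is no sample-size or power figure to reproduce. The check compares thresholds and then the timing of the measurements.

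**1. Range that triggers footnote b.** Grade 3 starts above 3.0 x ULN and Grade 4 above 10.0 x ULN (Table (8.12) 1). The SAP (section 4.2.3.4, CTCAE grade table) grades against baseline when baseline is abnormal: Grade 3 is above 3.0 x baseline, with baseline above ULN. Since 3.0 x baseline > 3.0 x ULN, the value is still above 3.0 x ULN.

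**2. Range in which section 6.1.2 allows an infusion.**

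| Patient | Allowed at infusion | Value at the time footnote b is triggered |
|---|---|---|
| No Gilbert's | total ≤ 1.5 x ULN | > 3.0 x ULN, i.e. more than 3.0 / 1.5 = 2 times the limit |
| Known Gilbert's | total ≤ 3.0 x ULN and direct ≤ 1.5 x ULN | > 3.0 x ULN, above the limit on total |

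The ranges do not overlap, so any value high enough to trigger footnote b would fail section 6.1.2 if it were also the pre-dose value.

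**3. Are they the same measurement?** Not necessarily. A note under Table (8.12) 1 bases dose changes on the worst toxicity so far, whereas section 6.1.2 tests the value before the next infusion. Two illustrative courses, without Gilbert's:
- Peak of 4 x ULN after D2, 1.4 x ULN before D9: footnote b lowers the dose and section 6.1.2 is met (1.4 ≤ 1.5). No conflict.
- Peak of 4 x ULN after D2, still 4 x ULN before D9: footnote b permits a reduced infusion and section 6.1.2 forbids it (4 > 1.5). Conflict.

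The conflict therefore requires bilirubin still above the section 6.1.2 limit when an infusion is due.

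**4. Does another passage settle it?** The asterisked note to the table is attached to the Grade 2 row and concerns Gilbert's patients enrolled with raised baseline bilirubin, so it does not resolve Grade 3–4 rises. Section 6.1.2 and the synopsis both point to Table (8.12) 1, but only for checking laboratory values for toxicity. Footnote b does not point back, and no passage says which prevails.

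**5. Effect on DLT evaluability.** Table (4.1.3.5) 3 requires at least 3 of the 4 cycle 1 infusions. One withheld infusion leaves 4 − 1 = 3, still enough; two leave 4 − 2 = 2, too few. But Table (4.1.3.5) 1 counts any Grade 3 or higher event as a DLT under its other-events row, provided it is at least possibly related. It also counts failure to restart at the same dose because of drug-related toxicity. Section 10.2.6 keeps a patient who has had a DLT in the data whatever the number of infusions. So a related rise ordinarily leaves the patient evaluable under either reading. The exposure rule bites mainly when the rise is judged unrelated and at least two infusions are withheld, and a non-evaluable patient in escalation is replaced (sections 4.1.3.3 and 4.1.3.5).

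**The case against.** The strongest reply is that the two rules work in sequence. Section 6.1.2 is a gate before each infusion; Table (8.12) 1 sets the dose level and decides who must stop. On that reading footnote b only replaces discontinuation with a one-level reduction, and treatment continues once the gate is passed. The footnote is discretionary and never orders an infusion on a given day, so a site that waits and then infuses one level lower breaches neither text. The Grade 3 row fits this: recovery to Grade 1 means at most 1.5 x ULN when baseline is normal, the same limit as section 6.1.2.

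This reading is possible, but it is not written. Footnote b says *continue*. Elsewhere the table states the wait explicitly: the Grade 2 and 3 bilirubin rows hold the drug until recovery, the AST/ALT rows hold until the value is back to 3 x ULN (the section 6.1.2 limit for those enzymes), and footnote e makes restart conditional on resolution. Footnote b alone in the isolated hepatic rules lets treatment go on after a Grade 3 or 4 value without such a condition. A site following it literally would be within its terms.

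Part of the reply stands. The contradiction covers only rises that persist to the infusion, and the pre-infusion lists already refer to the table, so only the return reference and a statement of precedence are missing.

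**Conclusion.** The inconsistency is real but narrow. When an indirect-only Grade 3–4 rise persists above the section 6.1.2 limit at the time of an infusion, footnote b permits what section 6.1.2 and the synopsis forbid. This rests on reading footnote b as written, without an implied recovery condition. It is an inconsistency of wording, not a design choice.

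Two stronger readings are tempting but unsupported:
- A reader might infer that every footnote b patient is both to be dosed and not to be dosed. That treats the worst preceding value and the pre-dose value as one reading. The documents do not give the proportion still raised at infusion.
- A reader might infer that a fixed share of each cohort becomes non-evaluable. Dividing one patient by a cohort of three or six measures nothing without an incidence, which the documents do not give. A related Grade 3 or higher event would also ordinarily be a DLT that keeps the patient evaluable.

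Remaining practical reach is limited. SAP sections 1.3 and 1.3.1 say escalation was stopped and the expansion will not be conducted. What is left is any patient still on treatment, consistent classification of deviations, and any reuse of the table.

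**What to change.** Reconcile footnote b and the isolated-bilirubin rows of Table (8.12) 1 with section 6.1.2 and the synopsis, so that one rule states whether the pre-infusion bilirubin criterion still applies when footnote b is used. Add a cross-reference from footnote b to section 6.1.2. The choice of rule is clinical and belongs to the sponsor; none is proposed here.

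The cost is one sentence in an amendment or investigator clarification, with no extra tests or visits.

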9. OTHER ASSESSMENTS NOT SPECIFICALLY RELATED TO EFFICACY OR SAFETY

The assessments hereafter are applicable for dose escalation phase I part of **Arm A**. They could be refined for expansion phase II part (**sub-arms A1/ A2**) according to results observed in the dose escalation phase I part, as well as for **Arm B** according to the results of Arm A. They will be described in an amendment to the protocol.

9.1. Assessments related to inclusion criteria.

Not applicable

9.2. IMPs concentration measurements

9.2.1. Blood samples

Concentrations of S64315 and azacitidine administered in combination, and of potential metabolite(s) will be determined in plasma using high performance liquid chromatography (HPLC) with tandem mass spectrometry (MS/MS) detection, according to a separate bioanalytical sample analysis plan established with the dedicated analytical laboratory.

Blood samples should be collected from the arm opposite from the IMP infusion if peripheral access is used, or from another site, such as an arm, if the patient displays a central vein line for the IMP infusion.

The accurate date and time of sample collection will be recorded on documents provided with the lab kits associated to each visit, called the requisition forms. All problems associated with sample collection or processing should be noted on the requisition forms and reported to the Sponsor's monitor.

A blood sample should be collected immediately following an ECG performed due to an unexpected cardiac signal, to assess drug concentration.

- Dose escalation phase I part

For each patient, concentrations of S64315 and azacitidine administered in combination, and of potential metabolite in plasma, will be measured as described in Table (9.2.1) 1.

Each patient will have a total of 13 PK samples collected.

Table (9.2.1) 1 - Time points for drug concentration assessment during dose escalation phase I part

Once a week administration of S64315 in combination with azacitidine (28-day cycle)	
Number of blood samples to be collected (3 mL each)	13 samples
	S64315
	EoI**
S64315 LID1	4h after EoI
	24h after EoI
C1D2: Second azacitidine injection	Predose*
First S64315 infusion (within 2h ±10 minutes after azacitidine injection)	[Start of S64315 Injection]
	10 min after SoI

Once a week administration of S64315 in combination with azacitidine (28-day cycle)	
Number of blood samples to be collected (3 mL each)	13 samples
	S64315
	30 min after SoI
	EoI**
	30 min after EoI
	1h after EoI
	2h after EoI
	4h after EoI
	7h ±1h after EoI
C1D3: Third azacitidine injection	24h after EoI

SoI Start of Infusion

**i.e. 5-30 min before infusion/injection*

EoI End of Infusion

*** i.e. within 5 to 10 min before the EoI*

Detailed instructions for sample collection, processing, handling, and shipment of samples will be provided in a laboratory manual.

Residual plasma used for PK analysis (e.g. S64315 and azacitidine plasma concentration) may also be used for exploratory analysis. This could include using leftover plasma for protein binding analysis, metabolite profiling, co-medication PK analysis or exploratory biomarker analysis, if there are sufficient samples remaining. Plasma samples remaining from the analysis may be retained by the Sponsor for additional investigations (i.e. long-term stability, reproducibility).

- Expansion phase II part

Measurement of drug concentration during the expansion phase II part of the study will be determined according to results observed in the dose escalation phase I part.

9.2.2. Identification and transfer of samples

Each sample will be clearly labelled with a double identification (aliquots 1 and 2) and will be shipped with a requisition form. It will be clearly labelled with the centre number, the patient number, date and hour of collection. Aliquots 1 and 2 will have to be sent in different shipments.

All PK samples will be shipped to the logistic platform (shipments at approximately -80°C). The logistic platform will then ship the aliquot 1 sample to the analytical laboratories. Aliquot 2 will be at logistic platform on interim storage until Sponsor request. At the latest 3 months after bioanalytical report signature and upon request of I.R.I.S., the logistic platform and the analytical laboratory will be responsible for the destruction of the samples received.

9.3. Pharmacodynamics measurements

Exploratory biomarkers, i.e. assessments planned to improve the knowledge of the combination of S64315 with azacitidine and/or the disease are detailed in [Table \(9.3\) 1](#).

Table (9.3) 1 - Biomarker sample collection plan

Sample type	Visit / time points	Volume	Marker	Purpose
Blood samples (PBMCs or fixed/lysed blood samples)	L1D1: S64315 predose CxD1: azacitidine predose CxD2: azacitidine predose, S64315 predose, 1h and 24h ±2h EoI Any time in case of disease progression****	10 mL (EDTA K2 tube) at each time point	Bcl-2 family members protein expression	To characterize PD markers and identify potential predictors of efficacy
	L1D1: predose C1D1: azacitidine predose C2D1: azacitidine predose C3D1: azacitidine predose In case of CR and every 3 months during study treatment period after CR for MRD only Any time in case of disease progression****	10 mL (EDTA K2 tube) at each time point	Genomic alterations of Bcl-2 family members and cancer related genes Detection and quantification of residual leukemic cells by gene expression and genomic alterations	To assess potential mechanisms of treatment resistance To assess MRD
Blood samples	L1D1: S64315 predose C1D1: azacitidine predose C1D2: azacitidine predose, S64315 predose, 4h, 6h, 24h and 72h after EoI C1D9: predose and 24h after EoI C1D16: predose Other cycles: CXD1 Aza predose; CXD16 predose	According to local procedures (2 - 4mL maximum)	Absolute count of Total and B lymphocytes	To assess potential surrogate response marker of biological activity as additional evidence of MCL-1 response
Bone Marrow Aspirate (BMA)* (BMMCs or fixed/lysed BMA samples)	Baseline*** Any time in case of response (at least PR) In case of disease progression****	2-5 mL (EDTA K2 tube) at each time point	Bcl-2 family members protein expression	Exploratory analysis for potential predictive markers of response
	Baseline*** C2D1: predose C3D1: predose In case of CR and every 3 months during study treatment period after CR for MRD only Any time in case of disease progression****	2-5 mL (EDTA K2 tube) at each time point	Genomic alterations of Bcl-2 family members and cancer related genes Detection and quantification of residual leukemic cells by gene expression and genomic alterations	To assess potential mechanisms of treatment resistance To assess MRD
Archived BMB sample (and corresponding pathology report if needed)** (if available)	Before screening	FFPE tumour block or 15-20 unstained slides	Bcl-2 family members protein expression	To assess potential Bcl-2 family members expression due to prior therapy
BMB sample** (if available)	Baseline*** Any time in case of response (at least PR) In case of disease progression****	FFPE tumour block or 15-20 unstained slides	Bcl-2 family members protein expression	Exploratory analysis for potential predictive markers of response
				To assess potential mechanisms of treatment resistance

Sample type	Visit / time points	Volume	Marker	Purpose
Saliva sample	Baseline*** In case of CR	Patient kit	DNA/RNA sequencing	Comparator to allow identification of somatic DNA variants in tumour
Copies of karyotype reports (if available)	Diagnosis and/or baseline*** In case of disease progression****	N/A	Chromosomal abnormalities	To assess potential modifications in karyotypes

BMMCs: Bone Marrow-derived Mononuclear Cells; BMB: Bone Marrow Biopsy, PBMCs: Peripheral Blood-derived Mononuclear Cells; FFPE: Formalin-Fixed Paraffin-Embedded

CR: complete response; PR: partial response

*If enough material is available from the BMA performed for the evaluation of efficacy measurement (anti-leukemic activity)

** If enough material is available from the BMB performed for the evaluation of efficacy measurement (anti-leukemic activity)

***Before the first IMP administration

**** N/A for LID period

